2.2.3. Minimization of Risks

Research participants will be carefully screened to meet enrollment criteria. Participants meeting exclusion criteria will not be enrolled. The study participant informed consent will be presented with clear description of the study requirements and opportunity to have questions answered before enrollment will be provided. Once an event occurs, review of symptoms will be

ascertained daily until symptoms have resolved or for 18 days. Reporting of adverse events will be reviewed routinely and in accordance with regulatory guidelines (21CFR, GCP) by the Principal Investigator. Participants with occurrence of worsening symptoms or adverse events will be advised to stop the product and may seek medical attention and exit the study.

3. Study Objectives

The purpose of the present study is to evaluate 1) the impact of the Immune Support test product on the duration of symptoms of the common cold in adult participants and 2) the subjective experience of these participants related to general health, common cold symptoms, and personal experience with the product. [13, 18, 29, 32]

This will be evaluated based on the primary and secondary endpoints. These endpoints, the analysis populations, and their respective measures are described below. Further details on the methods for measuring the outcomes can be found in the Study Outcome Measures and Analysis Plan sections.

Primary Endpoint:

The primary endpoint will be time to freedom from cold symptoms, with the clock starting at the onset of the cold. Where the onset is defined as the point in time when the participant experiences 2 or more cold symptoms. The primary analysis will be a Kaplan-Meier analysis of time to absence of all symptoms, based on the participants' self-report. There is no control group for the primary analysis. [5]

Secondary Endpoint:

- Secondary endpoints involve the duration and severity of the separate cold symptoms.
- Comparison against the participant's normal behavior.
- Net Promoter Score.
- Adverse events will be summarized.
- An additional data presentation will consist of results from both Treatment and Control in similar studies appearing in the literature. There will be no formal statistical comparison of results from this study and historical studies.

4.Study Design

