The present study will be a single site, prospective, single arm observational study of minimal risk consisting of at least 200 participants who suffer from cold symptoms. The participants must meet additional inclusion/exclusion criteria (see Inclusion/Exclusion Criteria). Participants will begin taking the powder drink-mix at the onset of their cold symptoms. Onset is defined as the point in time the participant experiences 2 or more cold symptoms (cough, hoarseness, muscle ache, nasal drainage,

nasal congestion, scratchy throat, sore throat, sneezing, or an oral temperature greater than 37.7 °C (99.9 °F)). When the participant experiences 2 or more symptoms, they will report symptoms in the cold start form. If they meet the criteria for a cold, they will start completing the daily cold symptom diary prior to taking the test product. After consuming the product, the participant will complete the cold symptom diary daily until all symptoms resolve. Since none of the ingredients in the test product have been seen to provide relief from fever or pain, the participant will be allowed to take a pain reliever and fever reducer (e.g. ibuprofen or acetaminophen). If medication is taken, the participant will record this in their symptom diary.

Study enrollment and management will be decentralized, where participants do not visit an investigator or a clinic for clinical assessment. The participants will participate in the study at home. All data collected from during this study will be reported by the participant via eCRFs, eDiary, and other electronic data entries. If a visit is required, it will be conducted via remote contact by telephone.

4.1.Test Product

Overview:

Participants in this study will consume the test product twice a day (4-6 hours apart) at the onset of cold symptoms. The participant will mix one packet of the test product in 6-8 ounces of water. The test product will be delivered to the participants' residence in a single shipment consisting of an18-day supply (36 packets) of the test product. The study participant will mix the contents of the packet into 6-8 oz. of hot water and drink twice a day during the duration of the cold.

Below is the description of the test product and its ingredients.

Test Product

Description: Combining whole food sourced Vitamin C, Echinacea, Ivy Extract, Zinc, Ginger and Turmeric. This formula is designed to support the immune system while reducing the duration of cold.

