4.2. Required Behavior

If the participant is prescribed antibiotics or any other medications for any reason, they should report this prescription and they will be withdrawn from the trial as of the prescription date.

Participants are asked not to ingest or take any other form of cold remedy (over-the-counter (NyQuil/Dayquil/Cough Syrup/Cough Drops/EmergenC/Airborne/Zarbee's or any similar cold-relief product or prescription drugs) during the 18-day study period. If taken during the study duration the participant will record this as part of their diary and will be exited from the study.

Because none of the active ingredients are aimed at pain relief or reducing fever, participants will be allowed to take pain relievers/fever reducers (Advil/Tylenol or their equivalent).

Participants are asked to limit the consumption of alcohol beverages to less than or equal to two drinks per day and avoid recreational drugs or use of cannabis during the study period.

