4.3. Participation Period

Participants are expected to participate in the study for 18 days after the onset of the first cold. Onset is defined as the day that the participant experiences 2 or more cold symptoms. Participant will be exited once all symptoms have been resolved or at 18 days whichever is shorter. If no cold has started within 90 days of participant study start date (date the participant receives and records receipt of test product) participants will be exited from the study.

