4.4. Data Collection

All data in the present study will be self-reported by the participant and collected via their online portal (Hawthorne Effect Study Visit Management System (HE VMS). Participants will be asked to take the test product according to the instructions for use, complete study surveys and respond to study reminders during the course of the study. The instructions for use and study forms can be found in the appendix.

The primary endpoint will be time to freedom from cold symptoms, with the clock starting at the onset of the cold. The primary analysis will be a Kaplan-Meier analysis of time to absence of all symptoms, based on the participants' self-report. There is no control group for the primary analysis.

Secondary endpoints involve evaluation of the duration and severity of the separate cold symptoms. An additional data presentation will consist of results from both Treatment and Control in similar studies appearing in the literature. There will be no formal statistical comparison of results from this study and historical studies.

5. Study Population

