5.1. Selection of the study Population

The study population will consist of at least 200 participants who have completed the self-enrollment form and who meet the inclusion-exclusion criterion. The participants will otherwise be in good health.

The target sample size for this study is initially 200 participants, with a desired sample of 80 treated participants This sample size has been calculated to provide a reasonable estimate of the time to cold resolution, as further described in detail in the Statistical Considerations section.

At such time as 180 participants have been enrolled, the available data will be analyzed using a constant hazard model to determine if it seems realistic that the desired number of 80 treated participants will be met by the end of follow-up. If the expected number of treated participants is less than 80, the target sample size will be increased as needed, considering both the desire for 80 treated participants and the timelines of the trial sponsor. The actual outcomes of treated participants will not be considered in this analysis, merely whether or not enrolled participants have reported starting using the test product.

Enrollment will be stopped once the target number of participants have been enrolled; no further participants will be offered a place in the trial once the target sample size criteria has been met. All participants who have already been offered places, but who have not yet consented, will be allowed to participate as long as they have signed the study consent within 15 days and the total number of participants does not exceed 125% of the target (either 200 or the recomputed target if recomputation has been performed).

In order to ensure an age and sex distribution that is reasonably representative of the US population, enrollment may be stopped early in some age and sex groups.

Target population for this study are candidates who are in the general population who are seeking herbal remedies to reduce the duration of their common cold symptoms.

Participants will be enrolled from across the United States. No participants will be enrolled outside of the United States. It is expected that the geographical distribution of the participants enrolled in the study will correlate with the geographical distribution of the general population across the United States.

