Participants will be recruited via digital advertisements. Ads will target those who are prone to getting the common cold; travelers, healthcare providers, teachers, daycare workers, etc.

After clicking on an advertisement, potential participants will then be directed to a website where they will complete a screening questionnaire (See Appendix). The screening questionnaire will

automatically qualify or disqualify them for study participation. If the participant qualifies, she will be provided an informed consent. Upon completion of the informed consent they will be deemed enrolled in the study.

5.2.Inclusion/Exclusion Criteria

Prior to being enrolled, participants will fill out a screening questionnaire. The screening questionnaire will automatically qualify or disqualify them for study participation. The full screening questionnaire can be found in the Appendix.

Inclusion Criteria:

Adult candidates in the general population who are in good health and are seeking herbal remedies to reduce the duration of their common cold symptoms when they should arise. Participants will be deemed to be in good health if they do not report any of the medical conditions asked about in the screening questionnaire.

Exclusion Criteria:

- Age < 18 years old
- Unwilling to try the test product during their first cold experience in the trial
- Has any of the following medical conditions:
 - Allergy to any of the following ingredients: Echinacea, Ivy Extract, Camu Camu, Vitamin C, Ginger, Turmeric, Zinc or a known allergy to Guar Gum, Monk Fruit, Citric Acid, Natural Flavors.
 - Alcohol consumption more than 10 drinks per week
 - Chronic renal disease
 - Chronic liver disease
 - Known autoimmune or immunodeficiency disorders
 - Pregnant or breastfeeding

6.Study Evaluation

6.1.Study Procedures

- Candidates will review information about the study and complete a screening form.
- During the screening process, the participant will be asked questions regarding their symptoms and medical history to ensure that they meet the requirements to participate in this study. The potential participant will also be asked questions to ensure that they do not meet any of the exclusion criteria and meet all of the inclusion criteria.
- After successful screening (participant does not meet any exclusion criteria), participants will
 review and sign study informed consent.
- Upon verification of signed informed consent, participant will be enrolled into the study.

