- At time of enrollment, participant will be given access to the HIPAA compliant study portal.
 - The study portal provides access to study information, signed informed consent form, instructions for product use, frequently asked questions, study surveys, symptom diary, and data collection tools.
- Participant shall complete baseline assessments upon access to the portal.
 - Baseline assessment will include questions regarding the participants' demographics, medications, detailed information regarding previous colds, including treatment.
- To ensure that baseline assessments are completed before test product is used by the
 participant, study materials and study welcome package will be shipped to the participant once
 the clinical study manager/clinical operations coordinator confirms that the baseline assessment
 has been completed.
- The welcome package will include an information sheet that will outline instructions for their participation in the trial, the test product, disposable thermometer, and paper forms of the

- documents (paper form of study documents will be provided for real time data collection, in the event that the participant cannot log into the study portal to input data).
- Once the participant receives the test product, the participant will log into the study portal to acknowledge the receipt of the test product.
- Study start date will be the date of acknowledgement of receipt of test product.
- Participant will be sent weekly email reminders that remind them of their participation in the study. Once the participant indicates they are experiencing a cold. The participant will be reminded by email daily to complete their symptom diary.
- At the onset of their cold symptoms, the participant will complete the cold start form.
 - Onset is defined as the point in time the participant experiences 2 or more cold symptoms (cough, hoarseness, muscle ache, nasal drainage, scratchy throat, sore throat, sneezing, oral temperature greater than 37.7°C (99.9 °F)).
 - If fever is a symptom that the participant experiences, they will use the provided disposable thermometer to take their temperature and record it in the diary.
- If the participant meets all the criteria for a cold, they will start their symptom diary prior to taking the test product.
- After completing the surveys, the participant will take the test product. The participant will mix 1 drink-mix packet into 6-8 oz of water and consume the whole drink.

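### Pregnancy is asked about once, at web screening; nothing visible asks again before a first dose that may come up to 90 days after the product arrives

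*Combined protocol and SAP*

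**What the plan says.** Section 5.2 lists "Pregnant or breastfeeding" among the exclusions and applies them through a web questionnaire that qualifies or disqualifies the candidate automatically. In Appendix C, item 4 is the single yes/no question on this. The schedule in section 6.2 marks the Screening Survey in the screening column only. Section 2.2.3 offers this screening as a protection: "Research participants will be carefully screened to meet enrollment criteria. Participants meeting exclusion criteria will not be enrolled".

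The product is not taken at enrolment. It is shipped after the baseline form is complete and kept at home. Section 4.3 ends participation "If no cold has started within 90 days of participant study start date", and that start date is the recorded receipt of the product. When a cold begins, section 6.1 says "At the onset of their cold symptoms, the participant will complete the cold start form"; the diary and then the first dose follow. Section 4 describes the content of that form only by saying that "they will report symptoms in the cold start form".

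The plan does have some checks after enrolment. Participants prescribed any medication must report it, and "they will be withdrawn from the trial as of the prescription date" (section 4.2). The diary (Appendix E) tells participants to exit if they have taken another cold medicine or been prescribed something. Section 6.5 provides for a contact at 30 days with participants who have given no event information, to ask about a cold and whether they wish to, or should, continue.

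**The concern.** Most trials dose soon after eligibility is checked. Here the two are separated by consent, the baseline form, shipping and then a wait for a cold. Pregnancy is the exclusion most obviously able to change in that time. The measure that section 2.2.3 relies on is applied once, and for pregnancy it may no longer hold when the participant is exposed. Exposure can then last up to 18 days.

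What is at stake is participant protection and consistency between the exclusion and its use. No estimate or error rate is involved. The documents name no pregnancy-specific hazard, describe the ingredients as generally recognised as safe, and class the study as minimal risk.

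**Working it through.** **1. Each step before the first dose**

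| Step | Source | Pregnancy raised? |
|---|---|---|
| Screening form | Appendix C, item 4 | Yes, once |
| Baseline form | Appendix D | No |
| Instructions for Use | Appendix B | No |
| Weekly e-mails | Section 6.1 | Described only as reminders of participation |
| 30-day contact | Section 6.5 | Not named |
| Cold start form | Sections 4 and 6.1 | Form not visible; described as reporting symptoms |
| Daily diary | Appendix E | No |

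Section 4.4 states "The instructions for use and study forms can be found in the appendix", but the cold start form is not among the appendix pages available. The consent form and the welcome-package information sheet are not available either.

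**2. The plan's own figure**

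Section 7.2 expects 40% of 200 enrolled participants to have a cold: 200 × 0.40 = 80. This reproduces.

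**3. Wait from receipt to first dose**

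For its sample size check, section 5.1 says "the available data will be analyzed using a constant hazard model", so I use a constant hazard here.

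- Hazard: λ = −ln(0.6)/90 = 0.00568 per day.
- Median wait among treated participants: −ln(1 − 0.40/2)/λ = 39 days. The mean is 1/λ − 90 × 0.6/0.4 = 41 days.
- With 20% or 60% incidence the median is 42 or 35 days. With uniform onset it is 45 days.
- Share of treated participants dosing by day 30: (1 − e^(−30λ))/0.4 = 39%.

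The time since the screening question is longer than this by the unstated lag L from screening to receipt.

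**4. Expected number affected**

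The documents do not give the number of women of childbearing age (n), the yearly pregnancy rate (r) or L. I assume n = 50 to 100, r = 5% to 10% and L = 0 to 30 days. With μ = −ln(1 − r)/365, the expected number conceiving after screening and by first dose is

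n × ∫₀⁹⁰ λe^(−λt) [1 − e^(−μ(t+L))] dt.

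| L (days) | n = 50, r = 5% | n = 100, r = 10% |
|---|---|---|
| 0 | 0.12 | 0.47 |
| 14 | 0.15 | 0.63 |
| 30 | 0.20 | 0.81 |

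A question can only reach those who know. If recognition lags conception by a fixed delay, the pregnancies that become known between screening and dosing come from a window of the same length, moved earlier. The expected number newly known is therefore also 0.12 to 0.81.

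- Poisson chance of at least one: 1 − e^(−0.12) = 11% to 1 − e^(−0.81) = 56%.
- With 20% cold incidence the range is 0.06 to 0.42; with 60% it is 0.16 to 1.17.
- With 50 women and r = 2%, it is 0.05 at L = 0 and 0.08 at L = 30.
- A cruder count agrees: 25% to 75% of the 80 treated able to conceive, r = 2% to 10%, and the 41-day mean wait give 80 × 0.25 × [1 − 0.98^(41/365)] = 0.05 to 80 × 0.75 × [1 − 0.90^(41/365)] = 0.7 between receipt and first dose.

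**5. Would the 30-day contact close the gap?**

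Take the contact as 30 days from receipt, and suppose it asked about pregnancy and caught every case known by then. Two groups remain: those dosing by day 30 (window t + L), and those dosing later whose pregnancy became known after the contact (window t − 30). Together they come to 0.06–0.26, 0.08–0.33 and 0.10–0.40 for L = 0, 14 and 30. That is 56%, 52% and 49% of the totals above.

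**The case against.** The strongest objection is that the absence cannot be proved. The natural place for a repeat check is the cold start form, which is unseen, as are the consent form and the information sheet. This stands as a limit: the finding covers the visible text only. The Instructions for Use are visible, however, and say nothing about pregnancy.

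Second, the criteria govern enrolment, and the plan never promises a second check, so nothing is contradicted. That is correct; this is a design choice. Still, the plan already uses the diary to stop participants for other changes, so a check at onset would fit its own approach.

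Third, the size is mostly assumption. This also stands:

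- The top of the range needs all three assumptions at their maximum, including 100 women of childbearing age among 200 participants. That fits poorly with section 5.1, which aims for an age and sex mix reasonably like that of the US population.
- A 2% yearly rate takes the count below the 0.12 minimum.
- The count supposes that nobody who learns she is pregnant holds back on her own, or leaves because of a new prescription. It is therefore a ceiling on what the question could prevent.

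The procedural point does not depend on these figures.

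**Conclusion.** The concern holds on the visible text. One self-reported answer at screening is the only check on pregnancy, and the first dose can follow up to 90 days after receipt, plus the lag from screening to receipt. Under the stated assumptions and 40% cold incidence, 0.12 to 0.81 treated participants would be affected (0.06 to 1.17 across 20% to 60% incidence). The 30-day contact would leave about half of the cases even if it asked about pregnancy.

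No harm is demonstrated and the primary analysis does not change, so the change is worth making but not essential. Confidence is medium, because the cold start form and consent form were not available. The other medical exclusions are not part of this point.

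**What to change.** On the cold start form, before the first dose, ask: *Are you now pregnant or breastfeeding?* If yes, the participant takes no product and the investigator is told. Optionally add: *Has any other answer you gave at screening changed?*

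In the Instructions for Use, add: *Do not take the product, or stop taking it, and tell the study team if you are or become pregnant.* If the cold start form already asks, only this sentence is needed.

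The cost is one or two items on a form already completed at onset, and one sentence; there are no extra visits. Anyone held back has taken no product and so falls outside the ITT population defined in section 7.1. The loss from the desired 80 treated participants would probably be no more than one or two: at an expected 0.81, the chance of two or more is 20% and of three or more 5%. The number held back by the optional item cannot be computed from the documents. The question will not reach a participant who does not yet know she is pregnant.

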7.1. Study Outcomes Measures

Analysis populations:

The *intent to treat* (ITT) population consists of all participants who are consented, report the onset of cold symptoms, and have taken the test product at least once. The primary analysis will be in the ITT population.

Primary Endpoint:

• The primary endpoint will be time to freedom from cold symptoms, with the clock starting at the onset of the cold. Where the onset is defined as the point in time when the participant experiences 2 or more cold symptoms. The primary analysis will be a Kaplan-Meier analysis of time to absence of all symptoms, based on the participant's self-report. There is no control group for the primary analysis.

Secondary Endpoints:

- Secondary endpoints involve the duration and severity of the separate cold symptoms.
- Comparison against the participant's normal behavior.
- Net Promoter Score.
- Adverse events will be summarized.
- An additional data presentation will consist of results from both Treatment and Control in similar studies appearing in the literature. There will be no formal statistical comparison of results from this study and historical studies.

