13.1.3. Appendix C Screening Form

Screening

- 1. Are you at least 18 years old? (DOB?) (Y/N)
- 2. Have you ever been diagnosed with any chronic liver disease? (Y/N)
- 3. Have you ever been diagnosed with any chronic renal disease? (Y/N)
- 4. Are you pregnant or breastfeeding? (Y/N)
- 5. Do you have any allergies to any of the following? (Y/N)
 - a. Echinacea
 - b. Ivy Extract
 - c. Camu Camu
 - d. Vitamin C
 - e. Ginger
 - f. Turmeric
 - g. Zinc
 - h. Monk fruit
 - i. Guar Gum
 - j. Citric Acid
 - k. Natural Flavoring
- 6. Have you ever been diagnosed with an autoimmune or immunodeficiency disease? (Y/N)
- 7. Do you have more than 10 alcoholic beverages per week? (Y/N)
- 8. Are you willing to try the test product for relief of your symptoms? (Y/N)
- 9. Are you comfortable taking your own temperature with a digital thermometer? (Y/N)

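### Screening does not record current or chronic nasal, throat or cough symptoms, so people with chronic symptoms can enter the primary analysis and may not reach its all-symptoms-absent event by day 18

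*Combined protocol and SAP*

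**What the plan says.** **Screening.** Section 6.1 states that "the participant will be asked questions regarding their symptoms and medical history to ensure that they meet the requirements". Sections 5.1 and 5.2 say that the questionnaire will "automatically qualify or disqualify them for study participation", and section 5.2 adds that candidates are "deemed to be in good health if they do not report any of the medical conditions asked about" on it. The form in Appendix C has nine items: age, chronic liver disease, chronic renal disease, pregnancy or breastfeeding, allergy to product ingredients, autoimmune or immunodeficiency disease, alcohol, willingness to use the product, and comfort with a thermometer. Symptoms appear only in the willingness item: "Are you willing to try the test product for relief of your symptoms". The exclusion list in section 5.2 has no respiratory or nasal condition either.

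**After screening.** The baseline form (Appendix D) asks about past colds and what is taken for them. Study start is the day on which receipt of product is acknowledged (section 6.1), and no symptom check is described at that step. Onset is the presence of two or more listed symptoms (sections 4, 4.3 and 6.1).

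**Analysis.** The ITT population in section 7.1 needs consent, a reported onset and one dose. "The primary analysis will be a Kaplan-Meier analysis of time to absence of all symptoms", by self-report. Section 7.3 censors participants who still have symptoms at day 18.

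**The concern.** Sneezing, nasal drainage, congestion and cough are cold symptoms under the protocol, and they are also everyday symptoms for people with allergic rhinitis, chronic sinus disease or chronic cough. Such a person meets the onset rule because it does not ask that symptoms be new or worse than usual. The same person may not meet the event because it asks that every symptom be gone.

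The effect falls directly on the one number that the trial is meant to produce. There is no control arm in which the same mix of participants would appear, and sections 7.3 and 13 place no later filter on it. The estimate will also be displayed beside published cold trials, whose entry criteria may differ. Because chronic symptoms are not asked about on any form shown, the analyst could not identify these participants afterwards.

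**Working it through.** **1. The plan's own figure.** Section 7.2 expects 40% of 200 enrolled participants to have a cold: 200 × 0.40 = 80. This reproduces. The plan gives no expected median, and no power or precision target against which to set a bias.

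**2. Does any step close the gap?**

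| Step | Would it detect chronic symptoms? |
|---|---|
| Appendix C screening form | No item |
| Section 5.2 exclusions | No item |
| Appendix D baseline form | Usual symptoms during a cold only |
| Acknowledgement of receipt | No symptom check described |
| Onset rule | Any two listed symptoms, new or not |
| Appendix E diary | Starts at onset, so has no pre-cold level |
| ITT definition | Reported onset plus one dose |
| Cold start form | Not in the supplied text |

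**3. Size, as an illustration.** Let f be the share of the ITT population who do not resolve by day 18. Let S0(t) be the curve for true colds, assumed Weibull with median m and shape k. Assume no censoring before day 18. The observed curve is

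S(t) = f + (1 − f) S0(t).

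Setting S(t) = 0.5 gives S0(t) = (0.5 − f)/(1 − f), so the observed median is

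t = m × [ln(1/S0)/ln 2]^(1/k).

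For m = 7 and f = 0.10: S0 = 0.40/0.90 = 0.444 and ln(1/0.444)/ln 2 = 1.170. Then t = 7 × 1.170 = 8.19 days at k = 1, and 7 × √1.170 = 7.57 days at k = 2.

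| f | Of 80 | Median, k = 2 | Median, k = 1 | Unresolved at day 18, k = 2 | Unresolved at day 18, k = 1 |
|---|---|---|---|---|---|
| 0% | 0 | 7.00 | 7.00 | 1.0% | 16.8% |
| 5% | 4 | 7.27 | 7.55 | 6.0% | 21.0% |
| 10% | 8 | 7.57 | 8.19 | 10.9% | 25.1% |
| 20% | 16 | 8.33 | 9.91 | 20.8% | 33.5% |

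(The 5%, k = 1 value is 7.546, hence 7.5 to one decimal.) With m = 5, a 10% share gives 5.41 to 5.85 days; with m = 9, it gives 9.73 to 10.53.

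**4. Minor point: colds already under way.** Suppose a share g of 5% to 20% are a = 2 to 4 days into a cold when product arrives, with m = 7 and k = 2.

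- Clock at receipt: solve (1 − g) S0(t) + g S0(t + a)/S0(a) = 0.5. The median falls to 6.92 at the mildest setting and 6.43 at the most extreme.
- Clock at true onset, no allowance for late entry: for t ≥ a, solve S0(t) × [(1 − g) + g/S0(a)] = 0.5. The median rises to between 7.02 and 7.25.

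The effect is small and its sign depends on where the clock starts.

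**The case against.** The strongest reply is that this is a descriptive, decentralised study that means to enrol broadly. Section 11 already concedes that it relies on self-report and that no clinician reviews symptoms, and the plan rules out formal comparison with historical studies. The diary scores eight symptoms from before the first dose, and symptom-level medians are planned, so a symptom that does not clear would be visible. Baseline medications enter the covariate analyses where available. The share f has no basis in the documents. With 80 participants and no early censoring, the approximate 95% half-width of the median is 1.96/(2 × √80 × density at the median), about 1.1 days at shape 2 and 2.2 at shape 1. The shifts at 5% and 10% lie inside that.

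Part of this stands. The size is unknown, and at low shares the shift is smaller than sampling error. But a shift of this kind does not shrink with more participants. The diary can show that a symptom persisted, but without a pre-cold level it cannot separate a chronic symptom from a long cold. The medication items in Appendix D concern what is taken for a cold. Section 11 does not mention chronic symptoms.

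A reader might infer more: that such people will enter the analysis, that they can never become symptom-free, or that people enrolled mid-cold will seriously distort it. The documents do not support this. They show only that such people can enter, and seasonal allergy, for one, may clear within 18 days. On mid-cold entry, section 5.2 speaks of future symptoms, section 4.3 counts from study start to a cold, and section 6.1 puts receipt before the cold start form. The intent is onset after receipt; only a check is missing. The unseen cold start form may also ask for an onset date, although a date alone would not reveal chronic symptoms.

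**Conclusion.** The mismatch between section 6.1 and Appendix C is real, and nothing in the supplied text closes it. Followed as written, the plan lets people with chronic symptoms be counted as having a cold and leaves them unlikely to reach the event by day 18. The direction is upward for the median and the tail. On a 7-day true median the illustrative shift is about 0.3 to 0.5 days at 5%, 0.6 to 1.2 at 10% and 1.3 to 2.9 at 20%. It rests on assumed shares, an assumed Weibull curve and diaries kept to day 18; participants who stop reporting sooner are censored sooner, and the shift would be smaller.

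Unenforced onset after receipt is a minor addition. The point does not undermine the design, but it should be settled before enrolment because the missing information is hard to recover later.

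**What to change.** 1. Add two items to Appendix C or the baseline form: whether the candidate has cold symptoms now, and which nasal, throat, cough or sneezing symptoms the candidate usually or chronically has, recorded symptom by symptom.
2. State in section 6.1 that a qualifying cold must begin after the study start date.
3. Keep absence of all symptoms as the primary event. In section 7.3 and the SAP, pre-specify one sensitivity analysis that repeats the Kaplan-Meier estimate without participants who have recorded chronic symptoms. Counting those symptoms as resolved on return to their recorded usual level is an acceptable alternative, but the choice should be fixed before any outcome data are seen.
4. Report the number with recorded chronic symptoms beside the primary median.

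The cost is two form items, one sentence, one further analysis on a somewhat smaller set, and a few deferred enrolments.
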